### Model Checking & Diagnostics

- Distributional assumptions underlying the model used for analysis will be examined by obtaining a normal probability plot of the residuals and a plot of residuals versus the fitted values (i.e. checking the normality assumption and constant variance assumption of the model respectively).
- If there are any departures from the distributional assumptions, alternative transformations, such as data squared or square root of data, will be explored.
- Non-parametric analyses will be conducted if the normality assumption does not hold.

### Model Results Presentation

- The coefficients of the slopes for the day effect for each dose, along with corresponding 90% confidence intervals, will be used to determine whether steady state was achieved.
- If the interaction is not significant, then a single point estimate and corresponding 90% confidence interval for all dose levels pooled will be presented.
- Trough concentration levels collected pre-morning dose will be plotted by collection day and dose.

## **10. ADDITIONAL ANALYSES DUE TO THE COVID-19 PANDEMIC**

### **10.1. Study Population**

#### **10.1.1. Subject Disposition**

The ‘Summary of Subject Status and Subject Disposition for the Study Conclusion Record’ and the ‘Summary of Treatment Status and Reasons for Discontinuation of Study Treatment’ will include the reason withdrawal/discontinuation due to issues related to the COVID-19 pandemic. In addition, these two summaries will be repeated, with the reason for withdrawal/discontinuation categorised as related to COVID-19 pandemic, or non-related to COVID-19 pandemic. The summaries will be based on GSK Core Data Standards, and details are provided in [Appendix 10: List of Data Displays](#).

#### **10.1.2. Protocol Deviations**

In addition to the overall summary of important protocol deviations, separate summaries will be produced of important protocol deviations related to COVID-19, and important protocol deviations not related to COVID-19. A listing of non-important protocol deviations related to COVID-19 will also be produced.

### **10.2. Safety**

#### **10.2.1. Assessment of COVID-19 AEs**

A standardised MedDRA Query (SMQ) will be used to identify all COVID-19 AEs.

The incidence of AEs and SAEs (Fatal and Non-Fatal) of COVID-19, COVID-19 AEs leading to study drug discontinuation and COVID-19 AEs leading to study withdrawal will be obtained from standard AE and SAE summaries.

#### **10.2.2. Impact of COVID-19 Pandemic on Safety Results**

The following tables will be produced, showing the incidence rates for events occurring before or after the start of the COVID-19 pandemic. The phases (before and after the start of the COVID-19 pandemic) are defined in [Section 12.4.1.2](#):

- Summary of exposure adjusted incidence rates of adverse events
- Summary of exposure adjusted incidence rates by age
  
- Summary of COVID-19 assessments for subjects with COVID-19 Adverse events

The above displays will be based on GSK Core Data Standards. Details of the planned displays are presented in [Appendix 10: List of Data Displays](#).

## **12. APPENDICES**

### **12.1. Appendix 1: Protocol Deviation Management and Definitions for PK and Efficacy Population**

There are no pre-defined categories leading to exclusion from the PK population, but all protocol deviations will be reviewed on a case-by-case basis.

[figure not shown]
Any participant in the safety population who does not provide at least two evaluable overnight sputum samples will be excluded from the efficacy population. All other protocol deviations will be reviewed on a case-by-case basis.

## 12.2. Appendix 2: Schedule of Activities

### 12.2.1. Protocol Defined Schedule of Events

Period	Screening			Dosing						Follow-up	
	1	2	3	4	5 to 10	11	12 to 16	17	18	Early Withdrawal	19
Visit											
Day	(-9 to -3) A	-2 B	-1	1	2 to 7 C	8	9 to 13 C	14	15		28 (± 7)
Documentation of Positive GeneXpert and/or TB smear (TB clinic/site of initial diagnosis)	X										
Written Informed Consent	X										
Demography (including smoking history)	X										
Medical & Treatment History	X										
Inclusion/Exclusion/Eligibility Assessment		X									
Chest X-ray		X									
Physical Examination D	X			X	X	X	X	X	X	X	X
Vital Signs E	X	X	X	X	X	X	X	X	X	X	X
12-Lead ECG	X							X		X	X
Randomisation M		X									
Echocardiogram (may be conducted at any of the screening visits)		X								X S	X S
Blood PK F							X F	X	X	X	
Spot Sputum (confirm TB & adequate bacterial load) G	X										
Rifampicin Resistance Test (rapid) G (microscopy and GeneXpert tests may be repeated on an overnight sputum sample if needed)	X										
Haematology, Clinical Chemistry, Urinalysis H	X			X	X	X		X		X	X
Cardiac safety biomarkers T		X		X	X			X			
Urine Drug Screen I	X	X I									
HIV Test (and CD4 Count if HIV confirmed)	X										
CCI				X	X			X		X	
				X	X			X		X	
			X					X			
Hospital Admission	X B	X B									

Period	Screening			Dosing						Follow-up	
Visit	1	2	3	4	5 to 10	11	12 to 16	17	18	Early Withdrawal	19
Day	(-9 to -3) A	-2 B	-1	1	2 to 7 C	8	9 to 13 C	14	15		28 (± 7)
Overnight Sputum L	X	X	X	X	X	X	X	X			
IP Administration and Compliance Check N				X	X	X	X	X			
Mycobacteriology Assessments O		X	X					X			
Hospital Discharge									X	X	
Concomitant Medication		X	X	X	X	X	X	X	X	X	X
Adverse Events P				X	X	X	X	X	X	X	X
Point of Care Blood Glucose or HbA1c Q		X						X			

- a. The Visit 1 (day -9 to -3) time period will be up to a maximum of 7 days but will be kept as short as possible.
- b. Participants can proceed with the Visit 2 (day -2) assessments as soon as their Visit 1 (day -9 to -3) assessments have been completed i.e. Visits 1 and 2 may occur on the same day as long as the screening results are available in time for randomisation. Participants may be hospitalised during the entire pre-treatment period if the Investigator considers it advisable for reasons of safety or compliance.
- c. All events listed as occurring on Visit 5 (day 2) to Visit 10 (day 7) and Visit 12 (day 9) to Visit 16 (day 13) will be conducted each day during these visits.
- d. Height (m) will only be collected once at Visit 1 (day -9 to -3). A full physical examination will be performed at Visit 1 (day -9 to -3), with symptom-directed physical examinations at Visit 17 (day 14), Visit 19 (day 28) and Early Withdrawal Visit (EWV). Symptom directed physical examinations may be conducted as required during the study (visits 4 to 16). Requirements for the physical examination are specified in the SRM.
- e. Systolic blood pressure (SBP) and diastolic blood pressure (DBP) (mmHg), heart rate (beats per minute [bpm]), body temperature (°C), respiratory rate (breathes per minute) and weight (kg). To be performed within 4 hours prior to the first daily dosing on Visit 4 (day 1) through to Visit 17 (day 14) and within 4 hours before the time dosing would have occurred on Visit 18 (day 15). On days where the following assessments are done the order should be: vital signs before blood draws for PK or safety assessments.
- f. PKs will be performed as noted in the PK table. A single pre-dose PK sample will be collected on each of Days 12 & 13, and serial PK blood sampling will occur on Day 14 (see PK table below). At EWV a PK sample will be taken before the time of the planned daily dosing. If this is not possible, a spontaneous PK sample will be taken.
- g. Sputum smear microscopy and molecular rapid test for confirmation of Mycobacterium tuberculosis and rifampicin susceptibility (GeneXpert). If the first spot sputum or overnight sputum sample shows an unfavourable result, the tests may be repeated on a freshly collected spot sputum or overnight sputum sample and that result used instead.
- h. Refer to [Appendix 3](#) for details.
- i. Urine drug screen: cocaine, amphetamines and opiates. Urine drug screen can be repeated at Visit 2 (day -2) for participants who were not hospitalized at Visit 1 (day -9 to -3).
- j. **CCI**
- k. 
- l. Overnight sputum sampling may start at Screening visit (day -9 to -3) or on Visit 2 (day -2) and will continue daily until Visit 7 (day 4). Additional sampling will be conducted at visit 9 (day 6), Visit 11 (day 8), Visit 13 (day 10), Visit

15 (day 12) and Visit 17 (day 14). Sputum sampling will stop on the morning of Visit 18 (day 15). Sputum collection will start in the afternoons at 15:00 hours ( $\pm 1$  hour) and continue for 16 hours overnight. The 16-hour sputum sampling for each of the sampling days must be finished prior to the administration of the next day's IP. Overnight sputum collection may be collected as many times as required over the screening period until an eligible sample is obtained. Of the pre-treatment period samples collected, only the Visit 2 (day-2) and Visit 3 (day -1) overnight sputum samples will be used for the efficacy endpoint tests.

The day sputum collection starts reflects the day to which that sample applies. e.g. a sample whose collection starts on day 1 and ends on day 2, is designated as the day 1 overnight sputum sample (and results).

- m. Randomization may occur once all the screening results are available and the Investigator has determined that the participant is eligible for the trial.
- n. After the first dose of IP, subsequent doses of IP will be administered 23 to 25 hours after the previous dose.
- o. Minimum inhibitory concentration (MIC) and speciation of the infecting organism by polymerase chain reaction (PCR) will be estimated from a culture collected on a pre-treatment day (day-1 or day-2) and from the last available culture on a treatment day (day 14 or earlier, but not earlier than day 8). Drug susceptibility testing of *M. tuberculosis* for sensitivity to rifampicin with a molecular method will be tested at Visit 1. Susceptibility to INH, Rif, EMB and PZA will be tested on a culture grown from a baseline sample (day -2 or day -1). The analysis of any bacterial isolates sent to GSK, Spain for further characterisation in the event of MIC change will not be reported in the clinical study report and will be reported separately.
- p. Adverse events (AE) will be collected by the Investigator from the time a participant receives his/her first dose of IP through to the Visit 19 (day 28) Follow up Visit.
- q. CC
- r. [not used]
- s. Only to be performed on participants as determined by the dose escalation committee (DEC) or on participants with changes in clinical status warranting a follow-up echo in the opinion of the investigator. The DEC may decide to perform this assessment in additional cohorts within this study.
- t. Samples will be assayed for: Troponin I. The first two samples at least 24 hours apart, one during the screening phase and one prior to the first dose of study treatment. Day 14 sample window is  $\pm 24$  hours. Third sample to be taken on Day 3.

**PK sampling time and events table**

STUDY VISIT	Visit 15	Visit 16	Visit 17										Visit 18
STUDY DAY	Day 12	Day 13	Day 14										Day 15
STUDY HOUR B			0	0.5	1	1.5	2	3	4	6	8	12	24
Pharmacokinetic sampling C	X A	X A	X D	X	X	X	X	X	X	X	X	X	X

- A. Sample to be taken within 30 minutes pre-dose.
- B. All values are relative to the time of day that the study treatment is administered on Day 14.
- C. PK sampling is only to be performed on participants receiving GSK3036656. PK samples will not be taken from participants receiving Rifafour e-275 (or equivalent generic alternative).
- D. Sample to be taken within 10 minutes pre-dose

**PK Sample timing window allowances**

Sample timepoint	Sample collection window allowed
Pre dose	Not applicable (see footnotes above)
0h - 4h post	± 5 min
> 4h – 12h post	± 15 min
> 12h – 24h post	± 1 h

## 12.3. Appendix 3: Assessment Windows

### 12.3.1. Definitions of Assessment Windows for Analyses

Analysis Set / Domain	Parameter (if applicable)	Target	Analysis Window		Analysis Timepoint
			Beginning Timepoint	Ending Timepoint	
Safety, Efficacy	All	Day -3	Day -9	Day -3	Screening
Safety, Efficacy	All	Day -2	Day -2	Day -2	Day -2, Screening
Safety, Efficacy	All	Day -1	Day -1	Day -1	Day -1, Screening
Safety, Efficacy	All	Day 1	Day 1	Day 1	Day 1
Safety, Efficacy	All	Day 2	Day 2	Day 2	Day 2
Safety, Efficacy	All	Day 3	Day 3	Day 3	Day 3
Safety, Efficacy	All	Day 4	Day 4	Day 4	Day 4
Safety	All	Day 5	Day 5	Day 5	Day 5
Safety, Efficacy	All	Day 6	Day 6	Day 6	Day 6
Safety	All	Day 7	Day 7	Day 7	Day 7
Safety, Efficacy	All	Day 8	Day 8	Day 8	Day 8
Safety	All	Day 9	Day 9	Day 9	Day 9
Safety, Efficacy	All	Day 10	Day 10	Day 10	Day 10
Safety	All	Day 11	Day 11	Day 11	Day 11
Safety, Efficacy, PK	All	Day 12	Day 12	Day 12	Day 12
Safety, PK	All	Day 13	Day 13	Day 13	Day 13
Safety, Efficacy, PK	All	Day 14	Day 14	Day 14	Day 14
Safety, PK	All	Day 15	Day 15	Day 15	Day 15
Safety	All	Day 28	Day 21	Day 35	Day 28

**NOTES:**

- For data summarised by visit, the nominal visit description will be used. Unscheduled and withdrawal visit data will be slotted into a scheduled visit window, if no competing visit exists within the window. If there are multiple assessments within the same window which are not unscheduled visits, the earliest results will be used in the summaries.

## 12.4. Appendix 4: Study Phases and Treatment Emergent Adverse Events

### 12.4.1. Study Phases

Adverse events will be classified according to the time of occurrence relative to the start of study treatment.

Study Phase	Definition
Pre-Treatment	Date and Time $\leq$ Study Treatment Start Date and Time
On-Treatment	Study Treatment Start Date and Time $<$ Date and Time $\leq$ Study Treatment Stop Date and Time + 48 hours
Post-Treatment	Date and Time $>$ Study Treatment Stop Date and Time + 48 hours

#### 12.4.1.1. Study Phases for Concomitant Medication

Study Phase	Definition
Prior	If medication end date and time is not missing and is before start of study treatment
Concomitant	Any medication that is not a prior medication

##### NOTES:

- Please refer to [Appendix 7: Reporting Standards for Missing Data](#) for handling of missing and partial dates for concomitant medication. Use the rules in this table if concomitant medication date is completely missing.

#### 12.4.1.2. Phases of COVID-19 Pandemic Measures

Pandemic measures began in different countries at different times. A dataset containing the date when pandemic measures began, as determined by the GSK country Issue Management Teams (IMT), and available within the HARP reporting environment (arcomn folder), will be used to determine the start date of pandemic measures within each country. A copy of this dataset will be taken at the time of database freeze (DBF).

Adverse events will be summarised according to whether the onset date was before or after the start of the COVID-19 pandemic measures.

Pandemic Measures Phase	Definition
Before	AE onset date $<$ pandemic measures start date
After	Pandemic measures start date $\leq$ AE onset date

**12.4.2. Treatment Emergent Flag for Adverse Events**

Flag	Definition
Treatment Emergent	

• If AE onset date and time is after treatment start date and time and before treatment stop date and time + 48 hours, i.e.: Study Treatment Start Date and Time <math>\leq</math> AE Start Date and Time <math>\leq</math> Study Treatment Stop Date and Time + 48 hours.

**NOTES:**

- If the study treatment stop date is missing, then the AE will be considered to be Treatment-Emergent.

## 12.5. Appendix 5: Data Display Standards & Handling Conventions

### 12.5.1. Reporting Process

Software	

 
The currently supported versions of SAS software will be used.
 
	
Reporting Area	
HARP Server	: UK1SALX00175
HARP Compound	: arenv/arprod/GSK3036656/mid201214
Analysis Datasets	

 
Analysis datasets will be created according to legacy GSK Analysis and Reporting dataset standards.
 
	
Generation of RTF Files	

 
RTF files will be generated for SAC.
 
	

### 12.5.2. Reporting Standards

General

 
The current GSK Integrated Data Standards Library (IDSL) will be applied for reporting, unless otherwise stated: 
 
4.03 to 4.23: General Principles
 
5.01 to 5.08: Principles Related to Data Listings
 
6.01 to 6.11: Principles Related to Summary Tables
 
7.01 to 7.13: Principles Related to Graphics
 
 
 

Formats

 
GSK IDSL Statistical Principles (5.03 & 6.06.3) for decimal places (DPs) will be adopted for reporting of data based on the raw data collected, unless otherwise stated.
 
Numeric data will be reported at the precision collected on the eCRF.
 
The reported precision from non eCRF sources will follow the IDSL statistical principles but may be adjusted to a clinically interpretable number of DPs.
 

Planned and Actual Time

 
Reporting for tables, figures and formal statistical analyses: 
 
Planned time relative to dosing will be used in figures, summaries, statistical analyses and calculation of any derived parameters, unless otherwise stated.
 
The impact of any major deviation from the planned assessment times and/or scheduled visit days on the analyses and interpretation of the results will be assessed as appropriate.
 
 
 
Reporting for Data Listings: 
 
Planned and actual time relative to study drug dosing will be shown in listings (Refer to IDSL Statistical Principle 5.05.1).
 
Unscheduled or unplanned readings will be presented within the participant's listings.
 
 
 

Unscheduled Visits	

 
Unscheduled visits will not be included in summary tables or figures, unless the data has been slotted to a visit (Section 12.3).
 
All unscheduled visits will be included in listings.
 
	
Descriptive Summary Statistics	
Continuous Data	Refer to IDSL Statistical Principle 6.06.1
Categorical Data	N, n, frequency, %
Graphical Displays	

 
Refer to IDSL Statistical Principals 7.01 to 7.13.
 
	

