### 8.1.3. Haematology Stopping Criteria

IP will be discontinued for a subject if the following haematology stopping criteria are met (confirmed on two samples or at the discretion of the investigator in consultation with the medical monitor) and participants should be followed up until values are not clinically significant.

- A reduction in haemoglobin to below 8.0 g/dL; this criterion may be adjusted following DEC review (see Section 11).
- A reduction in neutrophil count to below 500/mm^3 ( $0.5 \times 10^9/L$ )

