

and GSK Medical Governance approval is granted (see below)
 
 
• If restart/rechallenge not allowed per protocol or not granted, permanently discontinue study treatment and continue participant in the study for any protocol specified follow up assessments
 
 
MONITORING:
 
For bilirubin or INR criteria:
 
 
• Repeat liver chemistries (include ALT, AST, alkaline phosphatase, bilirubin) and perform liver event follow up assessments within 24 hrs
 
• Monitor participants twice weekly until liver chemistries resolve, stabilize or return to within baseline
 
• A specialist or hepatology consultation is recommended
 
 
For All other criteria:
 
 
• Repeat liver chemistries (include ALT, AST, alkaline phosphatase, bilirubin) and perform liver event follow up assessments within 24-72 hrs
 
• Monitor participants weekly until liver chemistries resolve, stabilize or return to within baseline
 
	
 
• Record alcohol use on the liver event alcohol intake case report form (CRF) page
 
 
For participants on GSK303656 arm
 
 
• Viral hepatitis serology
 
• Obtain blood sample for pharmacokinetic (PK) analysis as soon as possible, and certainly within 14 days after last dose
 
• Serum creatine phosphokinase (CPK) and lactate dehydrogenase (LDH).
 
• Fractionate bilirubin, if total bilirubin <math>\geq 2 \times \text{ULN}</math>
 
• Obtain complete blood count with differential to assess eosinophilia
 
 
For bilirubin or INR criteria:
 
For participants on GSK303656 arm only
 
 
• Auto-immune screen: Anti-nuclear antibody, anti-smooth muscle antibody, Type 1 anti-liver kidney microsomal antibodies, and quantitative total immunoglobulin G (IgG) or gamma globulins.
 
• Serum paracetamol/acetaminophen adduct high performance liquid chromatography (HPLC) assay (quantifies potential acetaminophen contribution to liver injury in participants with definite or likely acetaminophen use in the preceding week [James, 2009]).
 
• Liver imaging (ultrasound, magnetic resonance, or computerised tomography) and /or liver biopsy to evaluate liver
 

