### 5.2. Baseline Definitions

For all endpoints, except those noted below, the baseline value will be the latest pre-dose assessment with a non-missing value, including those from unscheduled visits (e.g. if Day 1 (pre-dose) is missing, Day -1 will be used). If there are no pre-dose data, then no derivation will be performed, and baseline will be set to missing.

For bacterial endpoints, baseline will be calculated as the mean of Day -2 and Day -1; if data are available at only one of these timepoints then that value will be used as baseline (i.e. data prior to Day -2 will not be used for calculation of baseline, even in the event there is missing data for both Day -2 and Day -1).

Unless otherwise stated, the mean of replicate assessments at any given time point will be used as the value for that timepoint.

If time is missing, Day 1 assessments are assumed to be taken prior to first dose and used as baseline.

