**12.6. Appendix 6: Derived and Transformed Data**

**12.6.1. General**

Multiple Measurements at One Analysis Time Point

 
• Mean of the measurements will be calculated and used in any derivation of summary statistics but if listed, all data will be presented.
 
• If there are two values within a time window (as per Section 12.3.1) the earliest value in that window will be used.
 
• Participants having both High and Low values for Normal Ranges at any post-baseline visit for safety parameters will be counted in both the High and Low categories of “Any visit post-baseline” row of related summary tables. This will also be applicable to relevant Potential Clinical Importance summary tables.
 

Study Day

 
• Calculated as the number of days from First Dose Date:             
 
• Ref Date = Missing → Study Day = Missing
 
• Ref Date < First Dose Date → Study Day = Ref Date – First Dose Date
 
• Ref Date ≥ First Dose Date → Study Day = Ref Date – (First Dose Date) + 1
 
 
 

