## 12.10.7. Safety Tables

Safety: Tables					
No.	Population	IDSL / Example Shell	Title	Programming Notes	Deliverable
Adverse Events (AEs)					
3.1.	Safety	AE5B	Summary of All Adverse Events by System Organ Class, Preferred Term and Maximum Grade	ICH E3	SAC
3.2.	Safety	AE5B	Summary of All Drug-Related Adverse Events by System Organ Class, Preferred Term and Maximum Grade	ICH E3	SAC
3.3.	Safety	AE15	Summary of Common (>=5%) Non-serious Adverse Events by System Organ Class and Preferred Term (Number of Subjects and Occurrences)	FDAAA, EudraCT	SAC
Serious and Other Significant Adverse Events					
3.4.	Safety	AE16	Summary of Serious Adverse Events by System Organ Class and Preferred Term (Number of Subjects and Occurrences)	FDAAA, EudraCT	SAC
3.5.	Safety	AE5B	Summary of Adverse Events Leading to Permanent Discontinuation of Study Treatment by System Organ Class, Preferred Term and Maximum Grade	IDSL	SAC
3.6.	Safety	AE5B	Summary of Adverse Events Leading to Withdrawal from Study by System Organ Class, Preferred Term and Maximum Grade	IDSL	SAC
3.7.	Safety	AE20	Summary of Serious Fatal and Non-Fatal Drug-Related Adverse Events by Overall Frequency	Plain Language Summary requirements (PLS).	SAC
3.8.	Safety	PAN10	Summary of Exposure Adjusted Incidence Rates of Adverse Events Over Time Relative to COVID-19 Pandemic Measures		SAC
3.9.	Safety	PAN10	Summary of Exposure Adjusted Incidence Rates of Adverse Events Over Time By Age Relative to COVID-19 Pandemic Measures		SAC

Safety: Tables					
No.	Population	IDSL / Example Shell	Title	Programming Notes	Deliverable
Laboratory: Chemistry					
3.10.	Safety	LB1	Summary of Chemistry Changes from Baseline	ICH E3	SAC
3.11.	Safety	LB17	Summary of Worst Case Chemistry Results by PCI Criteria Post-Baseline Relative to Baseline	ICH E3	SAC
Laboratory: Haematology					
3.12.	Safety	LB1	Summary of Haematology Changes from Baseline	ICH E3	SAC
3.13.	Safety	LB17	Summary of Worst Case Haematology by PCI Criteria Post-Baseline Relative to Baseline	ICH E3	SAC
Laboratory: Urinalysis					
3.14.	Safety	UR1	Summary of Worst Case Urinalysis Results Post-Baseline Relative to Baseline	ICH E3	SAC
Laboratory: Hepatobiliary (Liver)					
3.15.	Safety	LIVER1	Summary of Liver Monitoring/Stopping Event Reporting	IDSL	SAC
3.16.	Safety	LIVER10	Summary of Hepatobiliary Laboratory Abnormalities	IDSL	SAC
ECG					

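### The SAP's bar on unscheduled results has no exception for worst-case safety tables, so a participant's worst value can go uncounted

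*SAP*

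**What the plan says.** SAP 12.5.2, on reporting standards, gives the general rule: "Unscheduled visits will not be included in summary tables or figures, unless the data has been slotted to a visit (Section 12.3"). It adds that listings carry every unscheduled visit.

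The slotting condition is in the notes to SAP 12.3.1: "Unscheduled and withdrawal visit data will be slotted into a scheduled visit window, if no competing visit exists within the window". The safety windows there are single days from Day 1 to Day 15, then one window of Days 21–35 for the Day 28 visit.

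Three places deal with more than one value:
- SAP 5.2 and the first bullet of SAP 12.6.1 take the mean of values at one time point.
- The second bullet of SAP 12.6.1 says that, with two values in a window, "the earliest value in that window will be used".
- The notes to SAP 12.3.1 also take the earliest, but only among assessments that are not unscheduled.

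The displays at issue include Table 3.13, "Summary of Worst Case Haematology by PCI Criteria Post-Baseline Relative to Baseline", and its counterparts for chemistry (3.11), urinalysis (3.14), hepatobiliary abnormalities (3.16), QTc (3.18, 3.20) and vital signs (3.22). None has a programming note on unscheduled data.

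The protocol generates such data. Appendix 7 asks for liver repeats within 24 hours or 24–72 hours, then: "Monitor participants weekly until liver chemistries resolve, stabilize or return to within baseline" (twice weekly for the bilirubin and INR criteria). Section 8.1.3 normally needs a second haematology sample, and "participants should be followed up until values are not clinically significant". Section 9.4.5 has clinically significant laboratory results repeated until they settle.

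**The concern.** Protocol 10.3.2 promises a summary of worst-case laboratory and vital-sign results by number and percentage of participants. A worst-case table should draw on every post-baseline value. Under SAP 12.5.2 it draws only on scheduled values and on unscheduled ones that happen to fall in an unoccupied window. Baseline is treated differently: SAP 5.2 takes the latest pre-dose value, "including those from unscheduled visits".

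The participants affected are those whose results prompted extra tests. The timing matters too. With the 45-hour half-life in Protocol 5.6, five half-lives are 5 × 45 / 24 ≈ 9.4 days, so Days 16–20 still lie within five half-lives of the Day 14 dose. Reduced red cell count is the first risk listed in Protocol 3.3.1, and the haemoglobin trend in the first-in-human study was measured at follow-up.

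**Working it through.** There is no sample-size or power figure to reproduce. The check sets each possible day against the windows and the schedule of activities.

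**Inputs.** Windows are from SAP 12.3.1. Scheduled laboratory days are Day 1, Days 2–7, Day 8, Day 14 and Visit 19 (Day 28 ± 7). Footnote C of the schedule makes Days 2–7 daily if read literally. A visit is counted as competing only if it includes the same test. This is the reading kinder to the plan, because Days 9–13 and 15 have visits but no laboratory draw.

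| Day of unscheduled laboratory result | Window | Scheduled test in it | Outcome |
|---|---|---|---|
| 1–8, 14 | own day | yes | not slotted |
| 9–13, 15 | own day | no | slotted, kept |
| 16–20 | none | – | dropped |
| 21–35 | Day 28 | Visit 19, if attended | dropped |
| after 35 | none | – | dropped |

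So 6 of Days 1–15 can take an unscheduled laboratory result. If there is only one draw in Days 2–7 (assumed on Day 3), the figure is 11 of 15.

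**Liver repeats on the first, second or third day after a scheduled trigger.**
- Daily draws: 9 trigger days × 3 = 27 combinations; 7 kept, 18 competing, 2 without a window.
- Single draw: 4 × 3 = 12; 9 kept.

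**Weekly liver follow-up for four weeks.**
- Daily draws: 9 × 4 = 36; 7 kept, 22 competing, 7 without a window.
- Single draw: 4 × 4 = 16; 3 kept.

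These are counts of possible days, not event rates. On a competing day within Days 2–8 a scheduled sample exists and may itself serve as the repeat.

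**Other data.** Vital signs are scheduled on every one of Days 1–15, so no unscheduled reading can be slotted there. An unscheduled ECG can be slotted on 14 of those 15 days, but the two extra tracings of a triplicate share the first one's window and meet the conflicting rules.

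**When a table entry changes.** The maximum over the retained values can never exceed the maximum over all values. The category therefore changes only if a dropped value is worse than every retained one and lies across a category boundary.

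*ALT (illustrative values; PCI limit ≥3×ULN, SAP 12.8.1).* Day 14 is 2.5, unscheduled Day 17 is 6, Visit 19 is 1.2, and all other retained values are below 3. The retained maximum is 2.5, so there is no flag. The maximum of all values is 6, so there should be one.

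*Haemoglobin (illustrative values; PCI low flag <75 g/L).* Day 8 is 78, a same-day repeat is 72, Day 14 is 80, and all other retained values are at least 75. Ignoring the repeat or taking the earliest gives 78. The mean gives (78 + 72) / 2 = 75.0. None of these is below 75, although 72 was observed. This also needs the separate flag for a fall of 25 g/L not to apply, that is, a baseline below 72 + 25 = 97 g/L. The 10.0 g/dL entry limit applies at screening, while baseline is the last pre-dose value. The case is therefore narrow but possible.

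**The case against.** The strongest reply is that little is lost, and much of it stands. A reader might infer that every repeat required by the stopping rules is dropped. The table shows otherwise: after a Day 8 trigger, repeats on Days 9, 10 and 11 are all kept. A reader might also infer that a recovered Visit 19 value replaces the peak. It does not, because a scheduled trigger value stays in the table. If Day 14 were already 3.5×ULN, a dropped 6×ULN would leave the ALT flag in Table 3.11 unchanged, and only the maximum in Figure 3.2 would be wrong.

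Nor do such events survive only in listings. Table 3.15 summarises liver monitoring and stopping events, and clinically significant laboratory changes are recorded as adverse events and summarised by maximum grade. Withdrawal visits have their own route under SAP 12.7.1.

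Three further replies are weaker:
- The slotting note opens by referring to data summarised by visit, so it may not have been meant for worst-case tables. But the bar in SAP 12.5.2 covers all summary tables and figures.
- The sponsor's display standards may use all values. They are not in the documents, and SAP 12.5.2 applies them only where nothing else is stated.
- The third bullet of SAP 12.6.1 counts high and low values at any post-baseline visit, including in PCI tables. It does not say that unslotted results qualify.

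**Conclusion.** The point holds in a limited form. As written, the SAP can understate the worst-case category for a participant whose worst result is unscheduled and falls on Days 16–20, after Day 35, on Days 21–35 with Visit 19 attended, or on the same day as a scheduled test. Listings and event tables keep the information but do not correct the worst-case count.

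Any error in the maximum or minimum runs in one direction. A reader might go further and call the safety tables materially biased towards safety. The documents do not support that, because they give no rate of unscheduled tests or of values that would cross a category. The size is therefore a set of exposed days and conditions, not a number of participants.

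The conclusion assumes that SAP 12.5.2 is followed as written, that a competing visit means one with the same test, and that Table 3.11 includes ALT against the limits in SAP 12.8.1.

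**What to change.** In SAP 12.3.1 and 12.5.2, state that worst-case, PCI, maximum or minimum, and abnormality displays use all post-baseline results, whether scheduled, unscheduled or from withdrawal visits. Name the displays: Tables 3.11, 3.13, 3.14, 3.16, 3.18, 3.20 and 3.22, and Figure 3.2. Figure 3.1 already has a note asking for all time points.

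Limit slotting to by-visit summaries. Reconcile the mean and earliest-value rules in SAP 5.2, 12.3.1 and 12.6.1, saying which applies to a same-day unscheduled repeat. Replicate ECGs and vital signs taken at one assessment may keep the mean if the SAP says so.

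The cost is a few sentences in the SAP and a change to a programming filter. No new data are needed, since every unscheduled result is already to be listed.
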